2.1.5. Statistical Analysis

PK parameters will be summarized using descriptive statistics by Cycle and dose level. No hypothesis testing between dose-levels will be performed. Examinations of dose proportionality will be conducted according to the method of [Smith \(2000\)](#).

2.1.6. Additional Analyses

Additional analyses may be performed to determine the effect of CYP3A inhibitors or inducers on PK as well as the effect of FR α levels on PK.

2.2. Immunogenicity Analysis

2.2.1. Immunogenicity Population

The immunogenicity population includes all patients who received at least one infusion of IMGN853 and have evaluable immunogenicity data.

2.2.2. Analysis of Immunogenicity Data

Anti-IMGN853 seroconversion refers to the development of detectable antibodies which bind to IMGN853 and is based upon positive results in both screening and confirmatory assays. If a patient tests negative at all visits (no seroconversion), then the patient will be classified as seronegative. If the patient is positive at one or more visits (seroconversion), then the patient will be classified as seropositive. Percentage of patients who screen positive for anti-drug antibodies (ADA), percentage of patients who confirm positive, and antibody titer data will be summarized by time point using descriptive statistics. All data will be presented in listings for each patient.

Time to seroconversion will be calculated for the patients who have confirmed positive ADAs during the study. A table of time to seroconversion will be provided. Additionally, a table of ADA titer over time, and a table for last titer will be provided, as well as the supporting listing.

Peak titer value is defined as the maximum titer value experienced by a patient during the study. A table of peak titer and time to peak titer will be provided, including summary statistics, specifically, median, mean peak tiers and minimum, maximum titers by dose level.

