6.2. PK Schedule

6.2.1. Schedule A

Blood samples for PK measurements will be taken in Cycles 1 and 3, at the following time points:

Day 1 – predose, and following completion of infusion at the following timepoints: 0-10 minutes, and 2, and 4 hours (± 10 minutes)

Day 2 – 24 hours after completion of infusion (± 2 hours)

Day 3 – 48 hours after completion of infusion (± 2 hours)

Day 4 or 5, Day 8 and Day 15 – a single blood sample will be drawn for PK (±24 hours)

Additionally, a single pre-dose sample will be collected before the IMGN853 infusion and following completion of the infusion in Cycles 2, 4, 5 and 6. A single blood sample for analysis of HAHA and HADA will be taken on Day 1 of Cycles 2, 4, and 5 and at the End of Treatment and Follow-up visits.

The sample for HAHA and HADA analysis will be taken from the PK tube; no additional blood draw is necessary.

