6.3. Immunogenicity Assessments

To assess for potential immunogenicity against IMGN853 or DM4, plasma samples taken for PK assessment in cycles 1 through 6 will be taken as outlined in Sections 6.2.1 and 6.2.2, using the same tube that is used for the PK assessment. The study will evaluate the potential impact of immunogenicity on PK, Pd, safety, and efficacy of IMGN853 and total M9346A antibody. Specifically, clinical characteristics such as PK, safety and efficacy of immune positive patients will be compared to the immune negative population.

ImmunoGen, Inc. Confidential Page 81 of 138

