10.4. Cycle 3 Assessments

10.4.1. Cycle 3, Day 1

- Confirm that the patient satisfies all retreatment criteria (Section 5.9.3)
- Symptom-directed physical examination (Appendix A and Appendix B)
- Vital signs as outlined in Section 8.6, Appendix A and Appendix B
- Pulse oximetry (Section 8.8)
- Weight (Appendix A and Appendix B)
- ECOG performance status (Appendix A and Appendix B)
- Clinical laboratory tests (Section 8.10, Appendix A and Appendix B):
 - Serum chemistry
 - Hematology
 - Coagulation profile
 - o Urinalysis
- ECG performed in triplicate as outlined in Section 8.7.
- Directed neurological examination will be performed, to include light touch, pinprick, proprioception, and deep tendon reflexes (DTRs) of the upper and lower extremities; and questioning for symptoms of paresthesia and numbness (Appendix A and Appendix B).
 - o Neurotoxicity Questionnaire (FACT/GOG NTx), Version 4.0 (Appendix G)
- IMGN853 administration
- AEs and SAEs (Appendix A and Appendix B)
- Ocular symptom assessment (Section 5.8.8)
- Concomitant medications
- PK sample collection as outlined in Section 6 and Appendix C
- HAHA and HADA sample collection as outlined in Section 6

10.4.2. Cycle 3, Day 2

• PK sample collection as outlined in Section 6 and Appendix C

ImmunoGen, Inc. Confidential Page 100 of 138

- ECG performed in triplicate as outlined in Section 8.7
- Vital signs as outlined in Section 8.6, Appendix A and Appendix B
- Pulse oximetry (Section 8.8)
- AEs and SAEs (Appendix A and Appendix B)
- Concomitant medications

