1.4. Immunogenicity Assessments

Assessments for immunogenicity against IMGN853 were performed on plasma samples collected for PK assessments. This included samples collected prior to infusion on Day 1 of Cycles 1, 2, 4, and 5, at the End of Treatment and at Follow-up visits. The current analysis will evaluate the potential impact of immunogenicity on PK of IMGN853 and total M9346A antibody, specifically comparing IMGN853 and total antibody exposure between the immune positive and immune negative populations.

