2.1.4. Analysis of PK Data

All the PK analyses will be performed using the PK population, and will be conducted similarly for the Schedule A, Schedule B, and Dose Expansion cohorts. Initially, individual and mean concentrations for IMGN853, total antibody (TAb), DM4, and s-methyl-DM4 will be plotted vs. time by dose level for data collected in Cycles 1 and 3. The PK parameters listed in [Table 1](#) will be calculated from these data via standard non-compartmental methods ([Gabrielsso 2016](#)), and the results will be tabulated and summarized by Cycle and dose level. The PK data will be evaluated for dose proportionality and accumulation of each analyte will be assessed.

The observed concentrations for end of infusion in Cycles 2, 4, 5, and 6, as well as end of treatment and follow-up will be summarized and tabulated, but will not be analyzed further.

Table 1: PK Parameters to be Calculated from Data Collected in Cycles 1 and 3

PK Parameter	Definition
C_{\max}	Maximum plasma concentration observed
C_{last}	Final observed plasma concentration above LLOQ
AUC_{∞}	Area under the plasma concentration versus time curve extrapolated to infinite time
AUC_{last}	Areas under the plasma concentration versus time curve from time of dose until T_{last}
T_{\max}	Observed first time to reach C_{\max}
T_{last}	Time corresponding to the last concentration above the limit of quantification
$t_{1/2}$	Terminal half-life
CL	Clearance, i.e. volume of plasma that is completely cleared of the drug per unit time
V_{ss}	Volume of distribution at steady-state

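### Ever-positive ADA status is set against Cycle 1 and Cycle 3 PK, and by default against efficacy, without alignment in time; this dilutes the PK comparison and ties the efficacy comparison to time on treatment

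*SAP*

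**What the plan says.** The SAP file holds the main SAP and a separate PK and immunogenicity analysis plan (below, the PK plan).

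- **Grouping rule.** PK plan 2.2.2: "If the patient is positive at one or more visits (seroconversion), then the patient will be classified as seropositive". The other group is its complement: "If a patient tests negative at all visits (no seroconversion), then the patient will be classified as seronegative". No minimum number of samples is set, and a patient already positive before the first dose falls under the same label.
- **PK comparison.** PK plan 1.4 commits to "specifically comparing IMGN853 and total antibody exposure between the immune positive and immune negative populations".
- **Which PK.** PK plan 2.1.4: "Table 1: PK Parameters to be Calculated from Data Collected in Cycles 1 and 3". Concentrations from other cycles are tabulated only.
- **When ADA is tested.** PK plan 1.4: "samples collected prior to infusion on Day 1 of Cycles 1, 2, 4, and 5, at the End of Treatment and at Follow-up visits". Protocol 6.2.1 agrees for the later cycles: "A single blood sample for analysis of HAHA and HADA will be taken on Day 1 of Cycles 2, 4, and 5", plus the End of Treatment and Follow-up visits. Protocol 10.4.1 (Cycle 3, Day 1) nevertheless lists "HAHA and HADA sample collection as outlined in Section 6", although Section 6 names no Cycle 3 sample.
- **Efficacy and safety.** Protocol 6.3: "clinical characteristics such as PK, safety and efficacy of immune positive patients will be compared to the immune negative population". Main SAP 6.5 repeats the intention as exploratory. Neither defines immune positive or gives a method.

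**The concern.** The label is learned during follow-up and then applied to data collected before it was known.

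For PK, the question is whether antibodies lower exposure. If many profiles in the positive group were taken before the antibody existed, they look like those of negative patients and pull the difference toward zero. A reassuring result would then carry little information.

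For efficacy, a patient must stay on treatment to reach the Cycle 4 and Cycle 5 samples, and treatment generally continues until progression. The number of chances to test positive therefore depends on something close to the outcome. An ever-positive group gathers the patients who did well, which could hide a real loss of activity.

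**Working it through.** The plan gives no sample size, power or expected rate for the ADA comparison, so there is no figure to reproduce. ADA positivity rates below are assumptions.

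**1. Order of samples (PK plan 1.3 and 1.4)**

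C1 Day 1 pre-dose ADA → C1 PK profile → C2 Day 1 ADA → C3 PK profile → C4 Day 1 ADA → C5 Day 1 ADA → End of Treatment ADA → Follow-up ADA.

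- A patient not positive at baseline has the whole Cycle 1 profile before any post-dose test.
- Of five post-dose ADA visits, only Cycle 2 Day 1 precedes the Cycle 3 profile.
- A patient first positive at Cycle 4 or later contributes both profiles to the positive group, each taken before the first positive test.

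**2. Share of positive-group profiles taken before first detection**

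Among ever-positive patients with both profiles, let b be the share first positive at Cycle 1 pre-dose and c the share first positive at Cycle 2 Day 1. The first kind has no profile before detection, the second has one of two, and all others have two of two:

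share = 1 − b − c/2.

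With b = 0 the share is at least 0.5, because c cannot exceed 1. With baseline positives it can be lower. For a patient with six cycles, baseline rate 10% and later rate 2% per sample:

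- P(ever positive) = 1 − 0.90 × 0.98^5 = 0.186
- b = 0.10/0.186 = 0.536; c = 0.90 × 0.02/0.186 = 0.097
- share = 1 − 0.536 − 0.048 = 0.42

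| Baseline rate | Later rate per sample | Share before detection (six cycles) |
|---|---|---|
| 0% | 2% | 90% |
| 2% | 2% | 74% |
| 5% | 2% | 58% |
| 10% | 2% | 42% |
| 10% | 5% | 60% |

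The range crosses one half.

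**3. Illustration of the dilution in Cycle 3**

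Assume no baseline positives, first positives spread evenly over the post-dose visits, and no antibody effect before detection. A true 50% drop in Cycle 3 exposure would then appear as:

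- five post-dose visits: 1/5 × 50% = 10%
- leaving after Cycle 4 (four visits): 1/4 × 50% = 12.5%
- leaving after Cycle 3 (three visits): 1/3 × 50% = 17%

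These figures show the direction only, because all three assumptions are unsupported.

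**4. Chances to test positive by time on treatment**

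Scheduled samples, including Cycle 1 pre-dose: 3 for one cycle, 4 for two or three, 5 for four, 6 for five or more, with no rise after that. With k samples and independent positivity q per sample, P(ever positive) = 1 − (1 − q)^k.

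| q | One cycle (k = 3) | Five or more (k = 6) | Ratio |
|---|---|---|---|
| 1% | 3.0% | 5.9% | 1.97 |
| 2% | 5.9% | 11.4% | 1.94 |
| 5% | 14.3% | 26.5% | 1.86 |
| 10% | 27.1% | 46.9% | 1.73 |

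Two cycles (k = 4) against five or more gives smaller ratios: 11.4/7.8, about 1.47, at 2%, and 26.5/18.5, about 1.43, at 5%.

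The extra samples after infusion reactions (protocol 5.8.6 and 6.2.3) are not counted here. If they count as visits, a reaction itself raises the chance of being labelled positive. If a Cycle 3 Day 1 sample is in fact taken, patients reaching Cycle 3 have one more sample and two post-dose tests precede the Cycle 3 profile.

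**The case against.** A reader might infer that most PK in the positive group predates the antibody. The documents do not support that. Baseline positives count under the rule, their frequency is not given, and step 2 shows that the share can fall below half. Detection is also not onset: PK plan 1.4 lists no sample between Cycle 2 Day 1 and Cycle 4 Day 1, so an antibody first found at Cycle 4 may have been present during the Cycle 3 profile. For the same reasons, the 10% in step 3 cannot be read as an estimate of the attenuation.

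A reader might also infer that the plan specifies ever-positive groups for efficacy. It does not. The rule stands in the PK plan, which covers PK and immunogenicity; protocol 6.3 and main SAP 6.5 leave the grouping undefined. Applying the rule there is an inference, though a natural one, because no other definition exists.

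Some protection is planned. PK parameters are summarised by cycle, so Cycles 1 and 3 need not be pooled. Time to seroconversion, titer over time and patient listings are produced, and a PK-titer analysis is optional (PK plan 2.2.3). These let a reader see the timing, but none is linked to the positive-versus-negative comparison, and no landmark, time-varying status or split at first positive appears.

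The study tests no formal hypothesis, and its primary endpoints (MTD and RP2D) do not rest on this analysis. That limits the importance of the point without removing it.

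**Conclusion.** The point holds as a defect in an exploratory analysis. As written, PK taken before any positive test enters the positive group: all Cycle 1 PK in patients not positive at baseline, and Cycle 3 PK in patients first positive at Cycle 4 or later. If antibodies lower exposure only once present, the comparison is diluted toward no effect. The size cannot be fixed from the documents, since baseline positivity is not given and detection may lag onset.

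For efficacy the conclusion is conditional. If the ever-positive rule is used, patients with five or more cycles are about 1.7 to 2 times as likely to be labelled positive as those with one cycle, purely from sampling, at an assumed 1 to 10% per independent sample. Against two cycles the ratio is about 1.45 at 2 to 5%. The direction favours the positive group; the resulting bias in response or PFS is not quantified. It is worth correcting because the change is cheap.

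**What to change.** In PK plan 1.4 and 2.2.2/2.2.3:

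- Report baseline-positive and treatment-emergent ADA separately; a pre-dose positive is not a seroconversion.
- Compare Cycle 3 exposure, and the within-patient Cycle 3/Cycle 1 ratio at the same dose, by ADA status at the last sample before Cycle 3 dosing.
- Add a sensitivity analysis that counts patients first positive at Cycle 4 Day 1 as positive. Otherwise some with earlier onset sit in the comparator.
- Keep ever-positive status for incidence only.

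In main SAP 6.5 (and protocol 6.3), define immune positive and treat ADA as a time-dependent variable for efficacy and safety. Use a Cycle 2 Day 1 landmark only if enough patients are positive by then: at an assumed 3% per test, that is about 0.03 × 209 = 6 new positives across all doses and both schedules.

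Reconcile whether a Cycle 3 Day 1 ADA sample is taken (protocol 10.4.1 lists it; protocol Section 6 and PK plan 1.4 do not), and state whether samples after infusion reactions count toward ADA status.

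The cost is SAP wording and modest programming, with no new samples. The downside is that few patients will be classed positive in each comparison, so estimates will be imprecise and should be presented as such.

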2.5. Study Procedures

Secondary and exploratory objectives include characterization of PK, Pd, immunogenicity, FOLR1 levels, and other potential biomarkers in blood, tumor tissue, and biologic fluids that might predict response to IMGN853. Full profiles of blood samples for PK measurements were taken in Cycles 1 and 3 for all patients. Additionally, a single sample was collected pre-dose and following completion of the infusion in Cycles 2, 4, 5 and 6 for PK. A single blood sample for analysis of HADA and HAHA was taken on Day 1 of Cycles 2, 4, and 5

and at EOT and 28 day follow up visits, and three hours and 1 week following the onset of an IMGN853 infusion-related reaction. If PK sampling were performed concurrently, the HADA and HAHA samples were taken from the PK sample tube.

Ki67 IHC staining was assessed as a marker of cell proliferation on fresh biopsy samples from patients in Expansion Cohort 3.

All patients were genotyped for Fc γ R alleles via Peripheral Blood Mononuclear Cell (PBMC) analysis at screening.

Samples for Fc γ R were taken at screening. P-glycoprotein (PgP) IHC staining will be assessed in archived tumor tissues and on fresh biopsy samples obtained from patients in the expansion cohorts.

FOLR1 expression via a homocysteine-dependent upregulation of FOLR1 mRNA translation and plasma total homocysteine levels will be assessed in all patients at baseline, during Cycle 2, and at the end of treatment visit. Plasma methylmalonic acid (MMA) will be analyzed in parallel with plasma total homocysteine to differentiate folate and B12 status.

Exploratory biomarkers were collected pre-dose on the first day of each cycle and at other noted time points. Details can be found in [Sections 6](#) and [Section 7](#) of the study protocol.

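### The seroconversion rule in the PK and immunogenicity plan counts a confirmed antibody positive at the Cycle 1 pre-infusion visit, so pre-existing antibodies are classed as seroconversion

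*SAP*

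**What the plan says.** Section 2.2.2 of the PK and immunogenicity plan gives the concept first: "Anti-IMGN853 seroconversion refers to the development of detectable antibodies which bind to IMGN853", a finding that "is based upon positive results in both screening and confirmatory assays". It then gives two classification rules. For the negative class: "If a patient tests negative at all visits (no seroconversion), then the patient will be classified as seronegative". For the positive class: "If the patient is positive at one or more visits (seroconversion), then the patient will be classified as seropositive".

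Section 1.4 of the same plan states which samples were tested: "This included samples collected prior to infusion on Day 1 of Cycles 1, 2, 4, and 5", together with the end-of-treatment and follow-up visits. The first of these precedes any exposure.

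Section 2.2.2 promises a time-to-seroconversion table for patients with confirmed positive results, with no stated time origin and no exclusion of patients positive before dosing. It also promises screen-positive and confirmed-positive percentages and titres by time point, and listings for every patient. The immunogenicity population (section 2.2.1) needs one infusion and evaluable data; it does not need a paired baseline and post-dose sample.

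The other sampling lists differ. Protocol 6.2.1 says: "A single blood sample for analysis of HAHA and HADA will be taken on Day 1 of Cycles 2, 4, and 5". Protocol 6.2.2 and Appendix C footnote e name the same cycles, and main SAP 2.5 agrees: "A single blood sample for analysis of HADA and HAHA was taken on Day 1 of Cycles 2, 4, and 5". None of these four includes Cycle 1. Protocol 10.2.1, the Cycle 1 Day 1 procedures, does list an antibody sample. Protocol 6.3 and main SAP 6.5 speak of Cycles 1 through 6.

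**The concern.** Development implies a change after exposure. The rule applied to patients contains no change: one confirmed positive at any visit is enough, and one of the visits is before the first dose. The label and the rule therefore disagree for any patient with pre-existing antibodies.

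Characterizing immunogenicity is a secondary objective. What is at stake is the number of patients described as having seroconverted and the time-to-seroconversion table, which would mix patients who became positive on treatment with patients who were positive on arrival.

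The documents do not show that pre-existing antibodies occur. They do not rule them out either: protocol 3.1 lets dose-escalation patients have had earlier investigational compounds aimed at the folate receptor, and protocol 3.1.2 bars earlier monoclonal antibody treatment only where hypersensitivity is known.

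**Working it through.** The plan states no antibody rate, so there is no figure to reproduce. The check is of the text, followed by an illustration with assumed rates.

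**Text.** Take a patient confirmed positive before the Cycle 1 infusion and negative at every later visit.

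1. The pre-infusion Cycle 1 sample is an assessed visit (plan 1.4).
2. The patient is not negative at all visits, so cannot be seronegative (plan 2.2.2).
3. The patient is positive at one visit, so is seropositive and carries the seroconversion label (plan 2.2.2).
4. The patient has a confirmed positive, so enters the time-to-seroconversion table. The only positive sample precedes dosing, so the time is at or before first dose.

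No section of the plan, the main SAP or the protocol interrupts this chain with a negative-baseline condition. Elsewhere the main SAP does separate before from after: section 3.2 takes baseline from pre-dose Day 1, and section 6.2 counts an adverse event as treatment-emergent only if it starts on or after first dose. Antibody status has no matching rule.

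**Size.** Inputs:

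- *b*, the share of patients confirmed positive at baseline: assumed 2%, 5% and 10%.
- *i*, the share of baseline-negative patients who later become positive: assumed 5%. It applies to baseline-negative patients only.
- N = 209, the planned enrolment (main SAP 2.3.3). This is an upper limit, because the population needs evaluable immunogenicity data.

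Formulas:

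- Classed as seroconverted = 1 − (1 − b)(1 − i)
- Treatment-induced, as a share of all patients = (1 − b) × i
- Difference = 1 − (1 − b)[(1 − i) + i] = b

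| b | Classed as seroconverted | Treatment-induced | Difference | Patients (209 × b) |
|---|---|---|---|---|
| 2% | 1 − 0.98 × 0.95 = 6.9% | 0.98 × 0.05 = 4.9% | 2 points | 4.2 |
| 5% | 1 − 0.95 × 0.95 = 9.75% | 0.95 × 0.05 = 4.75% | 5 points | 10.45 |
| 10% | 1 − 0.90 × 0.95 = 14.5% | 0.90 × 0.05 = 4.5% | 10 points | 20.9 |

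The difference does not depend on *i*. If *i* were zero, every patient classed as seroconverted would have had the antibodies before treatment.

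**The case against.** The best defence has four parts.

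- **The displays show the baseline.** Positivity and titre are summarized by time point and listed per patient, so a Cycle 1 pre-dose positive appears in its own row. Section 2.2.3 also mentions change from baseline, among analyses that may be performed. This stands: a reader can find these patients. It does not alter their class or their place in the time-to-seroconversion table.
- **The word development already implies a negative baseline.** As a concept it does. The operative rule does not say so, and a programmer who follows it will include pre-dose positives.
- **There may be no Cycle 1 sample.** Four of the lists omit it. Plan 1.4 nevertheless reports it as collected, and protocol 10.2.1 schedules it. Without it, antibodies present before treatment could not be told apart from later ones at all.
- **The stakes are modest.** The study is descriptive, and MTD and RP2D do not depend on this rule. That is correct.

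A reader might also infer more than the documents support:

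- *That any positive screening result counts.* Both assays must be positive.
- *That the plan reports these antibodies as caused by the drug.* It does not say so; the implication comes only from equating positivity at any visit with development.
- *That a headline seroconversion rate will be inflated.* No seroconversion-rate table is explicitly promised, and the secondary endpoint is antibody levels.
- *That the exposure comparison will be diluted.* Plan 1.4 compares immune-positive with immune-negative patients without tying those groups to seroconversion. Whether pre-existing antibodies affect exposure is a fair question in itself, and neither direction nor size of any effect is shown.

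**Conclusion.** The point holds as a contradiction between a definition and its rule. As written, a patient confirmed positive only before dosing is classed as seroconverted and enters the time-to-seroconversion table with a time at or before first dose. The share classed as seroconverted exceeds the treatment-induced share by exactly the baseline prevalence.

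The documents do not give that prevalence. At an assumed 2% to 10% of up to 209 patients, about 4 to 21 patients are affected. The range assumes that all 209 are evaluable and that the Cycle 1 sample was tested. It counts every baseline positive as not treatment-induced, although some may show a titre rise on treatment. If baseline prevalence is zero, nothing changes.

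This should be corrected before the immunogenicity tables are produced. It does not touch the primary endpoints, and it does not mean that pre-existing antibodies would be concealed.

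**What to change.** In section 2.2.2 of the PK and immunogenicity plan:

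1. Define baseline antibody status from the pre-dose Cycle 1 sample.
2. Restrict seroconversion to patients negative at baseline with a confirmed positive after dosing.
3. Compute time to seroconversion in those patients only, measured from first dose.
4. Report baseline-positive patients as a separate group, with any titre rise over baseline shown descriptively.

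Then reconcile the sampling lists. Protocol 6.2.1, protocol 6.2.2, Appendix C footnote e and main SAP 2.5 omit Cycle 1; protocol 10.2.1 and plan 1.4 include it. Changing only protocol 6.2.1 and 6.2.2 would leave Appendix C and main SAP 2.5 in conflict.

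The cost is wording and a small programming change. Plan 1.4 reports the Cycle 1 sample as already collected, so no new sampling is needed on that account.
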